#### **7.5.3 Expedited Adverse Event Reporting Criteria to the IND Manufacturer**

#### **7.5.4 Reporting responsibility**

Each serious adverse event must be reported by the investigator to QED within 24 hours of learning of its occurrence, even if it is not felt to be treatment-related. Follow-up information about a previously reported serious adverse event must also be reported to QED within 24 hours of receiving it. If the serious adverse event has not been previously documented (new occurrence) and it is thought to be related to study drug (or therapy), the Medical Safety Expert of the Drug Safety & Epidemiology (DS&E) Department may contact the investigator to obtain further information. If warranted, an investigator alert may be issued, to inform all investigators involved in any study with the same drug (or therapy) that this serious adverse event has been reported.

*Abbreviated Title: BGJ398 in TIO*  
*Version Date: 21MAY2019*

### **7.5.5 Reporting procedures**

The investigator must complete the FDA MedWatch 3500a form and QED SAE report form in English, assess the relationship to study treatment and send the initial completed MedWatch form and QED SAE Report Form to Chiltern Pharmacovigilance via fax or email within 24 hours of becoming aware of the SAE. The original FDA MedWatch form and QED SAE report form must be kept with the case report forms at the study site.

Follow-up information should describe whether the event has resolved or continues, if and how it was treated, and whether the patient continued or discontinued study participation. The MedWatch form and QED SAE report form must be retained. Pregnancies

Any pregnancy that occurs during study participation should be reported. To ensure patient safety Within 24 hours of the site becoming aware of a pregnancy in either a study subject or the partner of a study subject, the Investigator is required to notify QED by completing the Pregnancy Notification Report and sending to Chiltern Pharmacovigilance via email (or) fax. The pregnancy should be followed up to determine outcome, including spontaneous or voluntary termination, details of birth, and the presence or absence of any birth defects, congenital abnormalities or maternal and newborn complications using the Pregnancy Follow-up Report form.

### **7.6 NIH OFFICE OF BIOTECHNOLOGY ACTIVITIES (OBA)/INSTITUTIONAL BIOSAFETY COMMITTEE (IBC) REPORTING CRITERIA: NOT APPLICABLE**

### **7.7 DATA AND SAFETY MONITORING PLAN**

#### **7.7.1 Principal Investigator/Research Team**

The clinical research team will meet on a regular basis, generally weekly, when patients are being actively treated on the trial to discuss each patient. Decisions about dose level enrollment and dose escalation if applicable will be made based on the toxicity data from prior patients.

All data will be collected in a timely manner and reviewed by the principal investigator or a lead associate investigator. Adverse events will be reported as required above. Any safety concerns, new information that might affect either the ethical and or scientific conduct of the trial, or protocol deviations will be immediately reported to the IRB using iRIS.

The principal investigator or designee will review adverse event and response data on each patient to ensure safety and data accuracy. The principal investigator will personally conduct or supervise the investigation and provide appropriate delegation of responsibilities to other members of the research staff.

#### **7.7.2 Sponsor Monitoring Plan**

This trial will be monitored by Clinical Research Associates (CRAs) employed by Rho, Inc on contract with NIDCR DIR, NIH. The CRA's are qualified by training and experience to monitor the progress of clinical trials. Personnel monitoring this study will not be affiliated in any way with the trial conduct. Clinical monitoring for this study will be guided by a Clinical Monitoring Plan that is developed jointly by the PI, OCTOM, the NIDCR Clinical Director and Rho.

The purpose of clinical monitoring is to ensure the rights of human subjects are protected, the study is implemented in accordance with the protocol, and the integrity of study data is maintained.

*Abbreviated Title: BGJ398 in TIO*  
*Version Date: 21MAY2019*

The monitoring plan will provide details about the monitoring activities including the frequency, procedures, and level of monitoring activities. Monitoring activities will include a study initiation visit, interim site monitoring visits, close out visit and, if necessary, for cause visits. Some monitoring activities may be performed remotely (e.g., review of regulatory documents), while others will take place on site (e.g., verification of study database entries against source documentation).

The frequency of interim monitoring visits will be based on patient accrual. Routine monitoring visits may be difficult to schedule on a regular basis due to unknown timing of patient accrual. A monitoring visit schedule, based on enrollment frequency, will be developed with the CRO and site staff in order to maximize oversight and minimize inconvenience to the site staff. If subjects can be scheduled in close time proximity, multiple subjects will be monitored at one visit.

### **7.7.3 Safety Monitoring Committee (SMC): Not Applicable**

### **7.7.4 Data Safety Monitoring Board (DSMB)**

The NIDCR Data and Safety Monitoring Committee (DSMC) will have oversight responsibilities for the study. The committee will include members with expertise in a broad range of areas, including human subject protection, research ethics, clinical trial implementation, biostatistics, and medical bone and mineral metabolism. In addition to any safety alerts, the DSMC will review data approximately twice a year related to enrollment progress, trial implementation, subject safety, and clinical efficacy. The DSMC will also consider current information from other sources on the biology of the disease, the investigational product, and the patient population under study. Based on these reviews, the DSMC will make recommendations to the principal investigator and the NIDCR clinical director concerning the continuation, modification, or termination of the trial. The roles and responsibilities of committee members and meeting procedures will be formally described in a charter.

The DSMC and the investigator will review the annual DSMC reports to determine whether the aggregate safety data should be reported to the FDA in an expedited manner.

Aggregate data will be reported in an expedited manner to the FDA if the DSMC or the investigator believes those data represent an unexpected set of related SAEs for which there is a reasonable possibility that they were caused by the study drug.

## **8 STATISTICAL CONSIDERATIONS**

### **8.1 STUDY POPULATIONS**

The safety and intent-to-treat populations are defined as all patients who received at least one dose of study drug.

The per protocol population is defined as the group of patients who complete the protocol without any major protocol deviations and have received 65% of study drug per cycle.

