### **3 STUDY IMPLEMENTATION**

#### **3.1 STUDY DESIGN**

Calcitriol (half-life is 5-8 hour) and phosphorous will be withheld for 3 days prior to the initiation of BGJ398 to allow for washout.

After initiation of study drug, subject will complete 24 weeks of BGJ398 with escalation/de-escalation of drug as described in Sections 3.1.2 and 3.3. Patients will return to the NIH every 4 weeks while on BGJ398 for an outpatient visit and labs per the schedule of events. Between monthly NIH visits, labs will be obtained per the schedule of events at the patients' local laboratories and results will be forwarded to the study team for review. In addition, any patient taking a concomitant medication associated with prolonged QT will obtain an EKG as an outpatient within 7-10 days after an increase in BGJ398 or the relevant concomitant medication. At the end of 24th week of BGJ398 treatment, subjects will be admitted as inpatients at the NIH for detailed laboratory and imaging evaluation as described in schedule of events. At the completion of the 24 weeks of treatment, patients who appear to have had a complete metabolic response will be evaluated at the NIH every 4 weeks for 3 additional visits. Complete metabolic response will be defined as normalization of blood phosphate and FGF23 levels after withdrawal of study drug. Local labs will be obtained in between NIH visits as clinically indicated on an as-needed basis. Subjects who have normal phosphate levels while on BGJ398 but have not had a complete metabolic response at the end of the 24 weeks of study drug may be considered for drug continuation in the extension phase, described in 3.1.3. Those who have not responded, have experienced significant side effects, or do not want to continue in the extension phase, will be terminated from the study and referred for other treatment.

During the active drug study period, subjects will not receive calcitriol and phosphorous supplements. However, subjects may be placed on calcitriol and phosphorous while in the post-BGJ398 drug monitoring phase or during dose interruptions, as clinically indicated. During the post-drug monitoring period calcitriol and phosphorous will be re-started on individual basis as clinically indicated (muscle weakness, bone pain, hypophosphatemia).

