### **3.7 SURGICAL GUIDELINES: NOT APPLICABLE**

### **3.8 RADIATION THERAPY GUIDELINES: NOT APPLICABLE**

### **3.9 COMPENSATION: NOT APPLICABLE**

### **3.10 CRITERIA FOR REMOVAL FROM PROTOCOL THERAPY AND OFF STUDY CRITERIA**

#### **3.10.1 Criteria for permanent removal from protocol therapy**

Subjects will be informed that they may choose to withdraw or the investigator may remove them from BGJ398 if it is in their best interest or if the subjects are unable to complete the required assessments and/or treatment. Voluntary withdrawal from the protocol is always an option for research participants.

The following conditions will require the permanent withdrawal of a subject from the BGJ398 therapy:

- Pregnancy
- Decline in calculated GFR to  $\leq 25$  mL/min/1.73 m^2 or decline in calculated GFR by 25 mL/min/1.73m^2 without clear etiology that persists on three monthly measurements (measured at the NIH or the subject's local laboratory).
- CTCAE  $\geq$  Grade 4 abnormalities in hepatic transaminases (ALT and AST)
- Treatment failure as defined by a blood phosphorus level below the lower limit of normal while taking the maximum tolerated dose of BGJ398 on two consecutive cycles.
- Investigator judgment based on subject's best medical interest

Subjects who require permanent discontinuation of BGJ398 therapy due to an adverse event will continue to be followed in the study until the toxicity has resolved or up to 30 days after study drug discontinuation. Pregnancies will be recorded from the time written informed consent is obtained until the subject is withdrawn from the study. Subjects who become pregnant during the study will be taken off BGJ398 and will be followed (with the subject's permission) until a pregnancy outcome is reached. The subjects will be referred to a physician outside of NIH for care. If the pregnancy results in anything other than a normal birth or elective abortion of a healthy fetus, it will be reported as an SAE. At the end of the pregnancy follow-up period, the subjects will be withdrawn from the trial.

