### **6.3.4 Duration of Response**

Duration of overall response: If complete metabolic response is achieved at the end of the 1 week end-of-study pharmacodynamic period (see section 3.4) following 24 weeks of BGJ398, the subjects will be followed for an additional 11 weeks ( $\pm$  2 weeks). If the subject has not had complete metabolic response at the end the 1 week end-of-study pharmacodynamic period or at any time during the follow-up, he/she will be offered the option of entering the extension phase or referred for alternative treatments.

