## **8.4 STATISTICAL ANALYSIS OF THE SECONDARY ENDPOINTS**

Secondary study endpoints will include:

- Complete metabolic response rate at the bi-weekly visits.
- Combined complete and partial metabolic response rate: partial response defined as both a decrease of at least 50% in FGF23 and an increase of at least 50% in phosphorus in the plasma at the bi-weekly, and 12-week follow-up visits.
- Biochemical measures of disease including plasma concentrations of FGF23, mineral panel, 1,25-(OH)2-Vitamin D, alkaline phosphatase, tubular reabsorption of phosphate, TRP, and TmP/GFR measured every 2 weeks.
- Eight quality of life domains from the RAND SF-36 survey measured at baseline and every 4 weeks.
- PROMIS survey measured at baseline and every 4 weeks
- Strength testing measured at baseline and every 4 weeks
- Six-minute walk test assessed at baseline, 24 weeks and 36 weeks.
- Radiographic evidence of TIO (in subjects with measurable tumor burden).

All analyses on the secondary endpoints will be performed on both the intent-to-treat and the per protocol populations.

Similar to the primary analysis, the complete response rate will be estimated with its exact 95% confidence limits, but at each bi-weekly sampling visit. The combined complete and partial response rate will be summarized as percent with its exact 95% confidence limits at every bi-weekly visit but with the 12-week follow-up visit rate of primary interest. Patients that for any

*Abbreviated Title: BGJ398 in TIO*

*Version Date: 21MAY2019*

reason are missing their response status will be counted as failures with respect to achieving complete or partial response.

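### The per-protocol set depends on an undefined completion condition that, on its ordinary reading, selects patients on response

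*Combined protocol and SAP*

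**What the plan says.** - **Section 8.1.** The per-protocol set is "the group of patients who complete the protocol without any major protocol deviations"; its members must also "have received 65% of study drug per cycle". The ITT set is "all patients who received at least one dose of study drug". Completion is not defined.
- **Section 3.1.** Once the treatment phase ends, "patients who appear to have had a complete metabolic response will be evaluated at the NIH every 4 weeks for 3 additional visits". For the others: "Those who have not responded, have experienced significant side effects, or do not want to continue in the extension phase, will be terminated".
- **Section 3.1.3.** Patients not in complete metabolic response at the end of the one-week pharmacodynamic period, or at any later point in follow-up, are offered study drug again if their phosphate normalised on it.
- **Section 6.3.4.** This restates the exit. A patient not in complete response at the end of that week "or at any time during the follow-up, he/she will be offered the option of entering the extension phase or referred for alternative treatments".
- **Section 3.10.1.** Permanent withdrawal from drug is required for, among other things, "Treatment failure as defined by a blood phosphorus level below the lower limit of normal while taking the maximum tolerated dose" on two consecutive cycles. The off-study criteria listed after it include having completed the follow-up period. They do not name treatment failure.
- **Section 8.3.** The primary complete response rate is assessed in ITT at the end of the 12-week follow-up (24 + 12 = week 36). Missing status counts as failure.
- **Section 8.4.** "All analyses on the secondary endpoints will be performed on both the intent-to-treat and the per protocol populations". These analyses include the combined complete and partial response rate, with the 12-week follow-up visit of main interest and missing status again a failure. They also include mixed models whose main contrast is baseline against that visit.

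**The concern.** A per-protocol set should be defined by conduct and exposure. Here one of its conditions is completion, and whether a patient stays in follow-up depends on response. If completion means being followed to the end, the patients counted at week 36 are those who were still responding at the visit before. The week-36 rate then no longer estimates how often the drug works.

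Counting missing status as failure does not help, because it acts only on patients in the denominator and those who left are outside it. Per-protocol rates at earlier visits would also be computed in patients chosen by what happened later.

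At stake are pre-specified secondary results: the per-protocol combined response rate at week 36 and the per-protocol baseline-to-week-36 contrasts for FGF23, phosphorus, 1,25-(OH)2-vitamin D and the strength and quality-of-life measures. With 10 patients, leaving the term open means its meaning could be settled after the responses are known.

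**Working it through.** **1. The plan's own figures.** Exact limits are Clopper-Pearson: lower = Beta quantile (0.025; x, n−x+1), upper = Beta quantile (0.975; x+1, n−x). For 5/10 this gives 18.71 to 81.29, against 18.7 to 81.3 in Table 8.4. Twenty of the table's 21 rows agree within rounding. The exception is the lower limit for 5/9 (21.2 computed, 21.1 printed), which has no bearing here.

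**2. Who is left at week 36 on the ordinary reading.** The three extra visits fall at weeks 28, 32 and 36. A patient not in complete response at about week 25 does not enter follow-up. A patient found to have lost response at week 28 or 32 is offered the extension or referred. So a patient counted at week 36 was in response at about week 32, and only a loss first seen at week 36 can lower the rate.

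**3. Counts.** The inputs are N = 10 and the hypothesised 40–60% response (section 8.5), so 4, 5 or 6 responders at week 36. First suppose that all other patients have left by rule. When x = n, the exact lower limit is 0.025^(1/n).

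| Responders | ITT (missing = failure) | Per protocol, no loss first seen at week 36 | Per protocol, one such loss |
|---|---|---|---|
| 4 | 4/10 = 40% (12.2 to 73.8) | 4/4 = 100% (39.8 to 100) | 4/5 = 80% (28.4 to 99.5) |
| 5 | 5/10 = 50% (18.7 to 81.3) | 5/5 = 100% (47.8 to 100) | 5/6 = 83% (35.9 to 99.6) |
| 6 | 6/10 = 60% (26.2 to 87.8) | 6/6 = 100% (54.1 to 100) | 6/7 = 86% (42.1 to 99.6) |

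The last column assumes that the extra patient meets neither response definition at week 36. If that patient still met the partial definition, the combined rate would stay at 100%.

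**4. What the rate measures.** Let p be the probability of response at week 25, and r the probability of losing it in each of the intervals 25–28, 28–32 and 32–36. The ITT rate is p(1−r)³. The per-protocol rate is p(1−r)³ ÷ p(1−r)² = 1−r, in which p cancels. The range of r is an assumption; p follows the plan.

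| r | ITT, p = 0.4 | ITT, p = 0.6 | Per protocol, either p |
|---|---|---|---|
| 0 | 40% | 60% | 100% |
| 0.1 | 29% | 44% | 90% |
| 0.2 | 20% | 31% | 80% |
| 0.3 | 14% | 21% | 70% |

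**5. The other reading.** If a rule-directed exit counts as completion, and all 10 patients meet the deviation and exposure conditions, those who left are in the set as failures. The per-protocol rate is then 5/10, equal to ITT. One gap remains: a patient withdrawn from drug for treatment failure before cycle 6 receives none in later cycles, and so fails a 65% condition applied to all six. With one such patient among the five non-responders the rate is 5/9 = 55.6%.

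**6. Mixed models.** On the ordinary reading, patients who exit contribute nothing to the per-protocol models. In ITT they contribute data up to exit but have no week-36 values. Redefining the set restores the earlier data and does not create the missing ones.

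**The case against.** The strongest reply is that leaving for the extension or for referral is a path the protocol itself lays out, so a patient who takes it has arguably completed the protocol. The rest of the 8.1 definition concerns conduct and exposure, not outcome. Section 6.3.3.3 grades complete response, partial response and progression at nine months, which presumes that non-responders are still assessed then. On that reading the per-protocol rate is about the ITT rate. This stands as a possible reading, but 8.1 does not adopt it, and the off-study criterion of having completed follow-up points the other way.

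A reader might infer that the per-protocol rate is 100% by construction. The documents do not support that:

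- Completion is undefined.
- A loss first seen at week 36 stays in the denominator.
- The extension is offered, not compulsory, and the plan does not say whether a patient who declines is still followed.
- Treatment failure in 3.10.1 ends drug therapy and is not listed as an off-study criterion.

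It is also fair to say that the week-36 complete response rate is the primary endpoint, defined in ITT. The per-protocol week-36 rate that 8.4 names is the combined one. Each per-protocol result will sit beside its ITT counterpart, so a divergence would be visible. That limits the harm but does not give the per-protocol figure a meaning.

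**Conclusion.** The point holds in a limited form. On the ordinary reading of 8.1 the per-protocol set is selected on outcome, and its week-36 combined response rate reflects only late loss of response, whatever the true response rate. At the plan's hypothesised 40–60%, that means 100% with no late loss, or 80–86% with one such patient, against 40–60% in ITT. The per-protocol baseline-to-week-36 contrasts carry the same selection.

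These sizes assume 10 treated patients, completion meaning follow-up to week 36, and patients without response actually leaving. If a rule-directed exit counts as completion, the excess largely disappears.

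A reader might also infer that the trial's main efficacy result is inflated. It is not: the primary endpoint uses ITT with missing status as failure, and the sample-size reasoning rests on the same basis. The definition should be corrected before the data are analysed.

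**What to change.** In 8.1, drop completion of follow-up as a condition. Define the per-protocol set by the absence of major deviations and by the 65% exposure criterion, applied to the cycles of the 24-week treatment period up to any protocol-directed exit. State that patients who exit for non-response, loss of response, treatment failure or entry to the extension stay in the set and count as non-responders at later visits. Limiting the exposure criterion to cycles before exit is needed; otherwise early treatment failures would still be excluded. Section 6.3.3.3 should be reconciled with 3.1, 3.1.3 and 6.3.4 on who is assessed at nine months. The exit rules themselves need no change for this purpose.

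The cost is a few sentences and no new data. The per-protocol rate becomes less favourable and closer to ITT, so it adds less as a separate result. The change does not supply week-36 values for the mixed models: patients who exit are missing there in ITT as well, and the report should say so.

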## **8.2 RACIAL, ETHNIC, AND GENDER MAKE-UP OF THE STUDY POPULATION**

Due to this limited pool of available TIO patients and an expected sample size of only 10 patients, all eligible patients will be enrolled without regard for their race, ethnicity, or gender. A listing of each patient's race, ethnicity, and gender will be reported. No sub-analyses or stratifications based upon race, ethnicity, gender, or other parameters are planned due to the small expected sample size.

## **8.3 STATISTICAL ANALYSIS OF THE PRIMARY OBJECTIVE AND ENDPOINT**

The primary objective is to induce a complete metabolic response in subjects with tumor-induced osteomalacia (TIO) with BGJ-398. The primary endpoint, complete metabolic response, is defined as the percent of patients in the ITT Population achieving both normal FGF23 and phosphorus levels in the blood at the end of the 12-week follow-up period. The complete response rate will be reported with its exact 95% confidence limits. Patients that for any reason are missing their response status will be counted as failures with respect to achieving complete response.

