## 1. INTRODUCTION

### 1.1 STUDY OBJECTIVES

#### 1.1.1 Primary Objective:

- To induce complete metabolic response in subjects with tumor-induced osteomalacia (TIO) with BGJ398 as demonstrated by normalization of FGF23 and phosphate homeostasis.

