#### 1.1.2 Secondary Objective:

- To evaluate the effects of BGJ398 on:
  - o mineral homeostasis
  - o quality of life
  - o muscle strength.
- To evaluate the effects of BGJ-398 on radiographic evidence of TIO.

**Table 1** summarizes the primary, secondary and exploratory objectives tagged with the associated endpoints and evaluation criteria:

	Objective	Endpoint Measures
Primary	Complete metabolic response	Normalization of blood phosphate and FGF23 off study drug
Secondary/Exploratory	Pharmacodynamics of mineral homeostasis response to BGJ398 in TIO	Changes in FGF23 (intact and C-terminal), Phosphorous, 1, 25 (OH) 2 vitamin D; TRP, TmP/GFR
	Effects on quality of life	Standardized measures of QoL
	Effects on muscle strength	Standardized muscle strength testing
	Effect on radiographic evidence of TIO	Changes in clinically-indicated FDG-PET/CT, octreotide SPECT/CT, or  Ga-DOTATATE PET/CT scan
	Assess safety/tolerability	Percentage of patients who incurred grade 3 or 4 adverse events (AEs) or serious adverse events (SAE) or AEs causing dose interruption/reduction

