### 3.1.3 Extension Phase

Subjects who do not demonstrate complete metabolic response at the end of the 1 week end-of-study pharmacodynamic period (see section 3.4) following 24 weeks of treatment or at any time during the follow-up period will be offered the opportunity to resume study drug at the maximum tolerated dose if they experienced normalization of blood phosphate levels while on BGJ398. They will be allowed to continue until either study closure, patient withdrawal, or, if in the judgement of the investigator, the adverse event profile of the subject outweighs the benefit. Subjects will continue to be monitored monthly for efficacy and safety. This will include monthly telephone follow-up to assess adverse events, monthly laboratory assessments and outpatient NIH visits at a minimum of every three months, to include an ophthalmologic examination.

*Abbreviated Title: BGJ398 in TIO*  
*Version Date: 21MAY2019*

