### **6.3.3.2 Evaluation of Non-Target Lesions**

Complete Response (CR): Normal FGF23 and phosphorous levels off drug are considered as complete metabolic response (CR).

Non-CR/Non-PD: Off drug decrease in FGF23 levels by 50% but still greater than the upper limit of the normal range and increase in plasma phosphorous levels by 50% but not to the normal range is considered as partial metabolic response.

Progressive Disease (PD): Increase in FGF23 levels, and decreased phosphorous levels (compared to that of baseline), off the drug is considered a progressive disease.

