### **6.3.3.3 Evaluation of Best Overall Response**

Best overall response is determined in terms of FGF23 levels and blood phosphorous levels at the end of 9 months (6 months on drug and 3 months off the drug).

Complete Response (CR): Normal FGF23 and phosphorous levels are considered as complete metabolic response (CR).

Non-CR/Non-PD: Off drug decrease in FGF23 levels by 50% but still greater than the upper limit of the normal range and increase in plasma phosphorous levels by 50% but not to the normal range is considered as partial metabolic response.

Progressive Disease (PD): Increase in FGF23 levels, and decreased phosphorous levels (compared to that of baseline), off the drug is considered a progressive disease.

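### Minor: the week-36 complete response rule sets no condition on phosphate or calcitriol, so a patient with normal FGF23 and supplement-supported phosphorus would count as a responder

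*Combined protocol and SAP*

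**What the plan says.** The primary objective (1.1.1) is a complete metabolic response "as demonstrated by normalization of FGF23 and phosphate homeostasis". Section 8.3 turns this into the percentage of the ITT population "achieving both normal FGF23 and phosphorus levels in the blood at the end of the 12-week follow-up period", reported with exact 95% limits.

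Four other places define the same response:

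- Table 1 (1.1.2): "Normalization of blood phosphate and FGF23 off study drug".
- Section 3.1: normal phosphate and FGF23 once study drug has been withdrawn.
- Section 6.3.3.2: "Normal FGF23 and phosphorous levels off drug are considered as complete metabolic response (CR".
- Section 6.3.3.3, at the end of 9 months: "Normal FGF23 and phosphorous levels are considered as complete metabolic response (CR".

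On supplements, section 3.1 bars calcitriol and phosphorus during active treatment but allows them in dose interruptions and after the drug is stopped. For the post-drug period it says "calcitriol and phosphorous will be re-started on individual basis as clinically indicated (muscle weakness, bone pain, hypophosphatemia".

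On loss of response, section 6.3.4 says that the patient "he/she will be offered the option of entering the extension phase or referred for alternative treatments", and section 3.1.3 says that patients whose phosphate normalized on drug "will be offered the opportunity to resume study drug at the maximum tolerated dose".

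The failure rules cover a missing response status (8.3) and withdrawal after the first dose (8.5).

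**The concern.** A phosphorus value held in the normal range by phosphate or calcitriol does not show that phosphate homeostasis has been restored, yet the scoring rule accepts it if FGF23 is also normal. No definition of complete response mentions supplements, and no failure rule covers them.

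The protocol already treats supplements as something to clear before measurement: they are stopped 3 days before the first BGJ398 dose (3.1, 4.2.4). Section 6.3.2 then compares off-drug levels with baseline. Baseline is therefore free of supplements, while the week-36 value need not be.

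A second, smaller gap lies in the same sentences. Section 8.3 and the complete response line of 6.3.3.3 leave out the off-drug condition that Table 1, 3.1 and 6.3.3.2 state.

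The primary result is at stake. The trial is open-label with one arm and about 10 patients, so the status of a single patient is visible in the rate, and it should not be settled after the data are seen.

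**Working it through.** **Step 1. Does any rule exclude a supplemented value?**

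| Place | Condition on BGJ398 | Condition on supplements |
|---|---|---|
| Table 1 (1.1.2) | off | none |
| 3.1 | withdrawn | none |
| 6.3.3.2 | off | none |
| 6.3.3.3, CR line | none | none |
| 8.3 | none | none |
| Failure rules, 8.3 and 8.5 | not applicable | none |

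In 6.3.3.2 the word drug most naturally means BGJ398, because Table 1 and 3.1 both say study drug. Sections 3.1.3 and 6.3.4 say what is offered to a patient who loses response. They do not say how a patient who stays in off-drug follow-up to week 36 is scored.

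**Step 2. Direction.** Adding a no-supplement condition can only remove patients from the set of responders. The rate under the written rule is therefore equal to or higher than the rate under the conditioned rule, never lower.

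**Step 3. Reproduce the plan's limits.** For x responders of n, the exact (Clopper-Pearson) limits are

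- lower = the 0.025 quantile of Beta(x, n - x + 1)
- upper = the 0.975 quantile of Beta(x + 1, n - x)

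All 21 rows of Table 8.4 reproduce to about 0.1 point. For 5/9 the lower limit computes to 21.20 against the printed 21.1, which is trivial.

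**Step 4. Size per patient.** One patient is 1/10 = 10.0 points at N=10 and 1/9 = 11.1 points at N=9. The documents give no count of such patients, so the range below is an assumption. It starts from 4 true responders, which at N=10 is the low end of the 40-60% hypothesized in 8.5.

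| Patients added | N=10 | N=9 |
|---|---|---|
| 0 | 4/10 = 40% (12.2-73.8) | 4/9 = 44.4% (13.7-78.8) |
| 1 | 5/10 = 50% (18.7-81.3) | 5/9 = 55.6% (21.2-86.3) |

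The first such patient raises the lower limit by 18.71 - 12.16 = 6.55 points at N=10 and by 21.20 - 13.70 = 7.50 points at N=9. With none, nothing changes.

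**The case against.** The strongest reply is that the affected group is close to empty. Section 1.2 names FGF23 as the driver of renal phosphate loss and low active vitamin D, and the first exclusion criterion removes other genetic or secondary causes of hypophosphatemia. A misclassified patient must have normal FGF23 and still be hypophosphatemic without supplements. Patient flow narrows this further. Under 3.1 the post-drug visits are for patients who appear to have responded, those who lose response are offered the extension or referred, and a missing week-36 status is a failure. TRP and TmP/GFR are also recorded (6.1) and supplements are logged (section 4), so such a case could be traced.

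Most of this stands, and it is why the point is minor. It does not close the gap. Restart is expressly allowed in the period that feeds the primary endpoint, the exit routes are offers and carry no scoring rule, and no scoring rule uses the traceable data.

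A reader might infer that non-responders kept on phosphate will generally be counted as responders. The documents do not support that: a patient with high FGF23 fails whatever the supplement use.

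Two of the three reasons given for restart are muscle weakness and bone pain. A scoring condition could therefore fail a patient whose homeostasis is truly restored. That cost is real and has to be reported.

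**Conclusion.** The point holds as a minor one. The written rule gives the wrong status to one narrowly defined kind of patient, and the error runs in one direction: 10 points per patient at N=10, 11.1 at N=9. Both the existence and the number of such patients are assumptions, and the number may be zero.

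Two stronger readings are tempting.

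- *A patient back on BGJ398 at week 36 could count as a responder.* The two sentences that omit the off-drug condition might suggest this. Table 1, 3.1 and 6.3.3.2 state the condition, and 6.3.3.3 itself places the assessment after 3 months off drug. The omission is a wording inconsistency to repair and does not set up a different endpoint.
- *Misclassification could carry the lower limit across a decision threshold.* Section 8.5 gives 18.7, 21.1 and 26.2% as lower limits that could justify therapy depending on toxicity. These are examples. The plan sets no threshold, so none is crossed.

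**What to change.** Change the scoring only, and leave the care of patients as it is.

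1. In 8.3 and 6.3.3.3, state that a complete responder has normal FGF23 and phosphorus at the week-36 sample, is off BGJ398, and took no phosphate or calcitriol within a pre-specified window before that sample. Otherwise the patient is a non-responder. The window could be the 3 days that the protocol already uses before the first dose. It is only an example: 3.1 gives a half-life for calcitriol but none for phosphate, and a patient who stopped long-term supplements just outside the window would still count.
2. In 8.4, apply the same supplement condition to complete response and to the phosphorus component of partial response at every visit where supplements are permitted, that is, in off-drug follow-up and dose interruptions. If it covers week 36 alone, the same patient could be scored under different rules at different visits. If it leaves out partial response, a reclassified patient could re-enter the combined rate.
3. Report one supportive rate that ignores supplement use, with a by-patient listing of supplement start and stop dates beside TRP and TmP/GFR.

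The cost is one sentence in each of two sections, one line in 8.4, one extra rate and one listing. No new data are needed, because concomitant medications are already on the eCRF. The downside is that a true responder taking supplements for bone pain or weakness is scored a failure in the primary rate. The supportive rate makes this visible.
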